#### **iRECIST Response Assessment**

Overall response will be assessed using immune Response Evaluation Criteria in Solid Tumors (iRECIST). Immunotherapeutics may result in infiltration of immune cells leading to transient increase in the size in malignant lesions, or undetectable lesions becoming detectable. The criteria are identical to those of Response Evaluation Criteria in Solid Tumors (RECIST) 1.1 in many respects but have been adapted to account for instances where an increase in tumor burden, or the appearance of new lesions, does not reflect true tumor progression.

#### Key differences are described below.

#### Comparison of RECIST 1.1 and iRECIST

	RECIST 1.1	IRECIST
Definitions of measurable and non-measurable disease; numbers and site of target disease	Measurable lesions are $\geq 10$ mm in diameter ( $\geq 15$ mm for nodal lesions); maximum of five lesions (two per organ); all other disease is considered non-target (must be $\geq 10$ mm in short axis for nodal disease)	No change from RECIST 1.1; however, new lesions are assessed as per RECIST 1.1 but are recorded separately on the case report form (but not included in the sum of lesions for target lesions identified at baseline)
Complete response, partial response, or stable disease	Cannot have met criteria for progression before complete response, partial response, or stable disease	Can have had iUPD (one or more instances), but not iCPD, before iCR, iPR, or iSD
Confirmation of complete response or partial response	Only required for non-randomised trials	As per RECIST 1.1
Confirmation of stable disease	Not required	As per RECIST 1.1
New lesions	Result in progression; recorded but not measured	Results in iUPD but iCPD is only assigned on the basis of this category if at next assessment additional new lesions appear or an increase in size of new lesions is seen ( $\geq$ 5 mm for sum of new lesion target or any increase in new lesion non-target); the appearance of new lesions when none have previously been recorded, can also confirm iCPD
Independent blinded review and central collection of scans	Recommended in some circumstances—eg, in some trials with progression-based endpoints planned for marketing approval	Collection of scans (but not independent review) recommended for all trials
Confirmation of progression	Not required (unless equivocal)	Required
Consideration of clinical status	Not included in assessment	Clinical stability is considered when deciding whether treatment is continued after iUPD
"i" indicates immune responses assigned using iRECIST. RECIST=Response Evaluation Criteria in Solid Tumours. iUPD=unconfirmed progression. iCPD=confirmed progression. iCR=complete response. iPR=partial response. iSD=stable disease.		
Table 1: Comparison of RECIST 1.1 and iRECIST		

All responses defined using iRECIST criteria are designated with a prefix. The iRECIST timepoint and best overall responses will be recorded separately.

#### Confirming progression

Unlike RECIST 1.1, iRECIST requires the confirmation of progression and uses the terms iUPD (unconfirmed progression) and iCPD (confirmed progression). Confirmatory scans should be performed at least 4 weeks but no longer than 8 weeks after iUPD.

iCPD is confirmed if further increase in tumor burden, compared to the last assessment, is seen as evidenced by one or more of the following:

- Continued increase in tumor burden (from iUPD) where RECIST 1.1 definitions of progression had been met in target, non-target disease, or new lesions
  - Progression in target disease worsens with an increase of at least 5 mm in the absolute value of the sum
  - Continued unequivocal progression in non-target disease with an increase in tumor burden
  - Increase in size of previously identified new lesion(s) (an increase of at least 5 mm in the absolute value of the sum of those considered to be target new lesions) or additional new lesions.

• RECIST 1.1 criteria are met in lesions types (target, non-target, or new lesions) where progression was not previously identified, including the appearance of additional new lesions.

If iUPD is not confirmed at the next assessment, then the appropriate response will be assigned (iUPD if the criteria are still met, but no worsening, or immune stable disease [iSD], immune partial response [iPR], or immune complete response [iCR] if those criteria are met compared to Baseline). Prior documentation of iUPD does not preclude assigning iCR, iPR, or iSD in subsequent timepoint assessments or as best overall response providing that iCPD is not documented at the next assessment after iUPD.

#### New lesions

New lesions should be assessed and measured as they appear using RECIST 1.1 criteria (maximum of 5 lesions, no more than 2 per site), at least 10 mm in long axis (or 15 mm in short axis for nodal lesions), and recorded as New Lesions-Target (NLT) and New Lesion-Non-Target (NLNT) to allow clear differentiation from Baseline target and non-target lesions.

New lesions may either meet the criteria of NLT or NLNT to drive iUPD (or iCPD). However, the measurements of target lesions should NOT be included in the sum of measures of original target lesions identified at Baseline. Rather, these measurements will be collected on a separate table in the Case Report Form.

Progressive disease is confirmed in the New Lesion category if the next imaging assessment, conducted at least 4 weeks (but not more than 8 weeks) after iUPD, confirms further progression from iUPD with either an increase of at least 5 mm in the absolute value of the sum of NLT OR an increase (but not necessarily unequivocal increase) in the size of NLNT lesions OR the appearance of additional new lesions.

# **Appendix 5 Abbreviations**

AE	adverse event
AESI	adverse events of special interest
ADL	Activities of Daily Living
ALT	alanine aminotransferase
ANC	absolute neutrophil count
AST	aspartate aminotransferase
BICR	Blinded Independent Central Review
BRAF	Gene encoding B-Raf protein
BUN	blood urea nitrogen
CFR	Code of Federal Regulations
CI	confidence interval
CNS	central nervous system
CR	complete response
CRO	Contract Research Organization
СТ	computed tomography
CTLA-4	anti-cytotoxic T-lymphocyte-associated protein-4
DILI	drug induced liver injury
DNA	deoxyribonucleic acid
DOR	duration of response
DTH	delayed-type hypersensitivity
ECOG	Eastern Cooperative Oncology Group
eCRF	electronic Case Report Form
EOS	end of study
FDA	Food and Drug Administration
FFPE	formalin fixed, paraffin embedded
FSH	follicle stimulating hormone
GCP	Good Clinical Practice
GMP	Good Manufacturing Practice
GM-CSF	granulocyte-macrophage colony-stimulating factor
hTERT	human telomerase reverse transcriptase
GOT	glutamic-oxaloacetic transaminase
GPT	glutamic-pyruvic transaminase
HIV	human immunodeficiency virus
HR	hazard ratio

HRT	hormonal replacement therapy
IB	Investigator's Brochure
ICF	Informed Consent Form
ICH	International Conference on Harmonisation
IDMC	Independent Data Monitoring Committee
IEC	Independent Ethics Committee
IMP	investigational medicinal product
IRB	Institutional Review Board
ITT	intention-to-treat
iCPD	immune confirmed progressive disease
iCR	immune complete response
iPR	immune partial response
iRECIST	immune RECIST
iSD	immune stable disease
iUPD	immune unconfirmed progressive disease
IWRS	interactive web response system
MedDRA	Medical Dictionary for Regulatory Activities
MEK	mitogen-activated protein kinase
MRI	magnetic resonance imaging
NE	non-evaluable
NIMP	non-investigational medicinal product
NLNT	New Lesion-Non-Target
NLT	New Lesions-Target
NSCLC	non-small cell lung cancer
ORR	objective response rate
OS	overall survival
PBMC	peripheral blood mononuclear cell
PD	progressive disease
PD-1	anti-programmed cell death
PFS	progression free survival
PR	partial response
RBC	red blood cells
RECIST	Response Evaluation Criteria in Solid Tumors
RNA	ribonucleic acid
Q2W	every 2 weeks
Q3W	every 3 weeks

Ultimovacs UV1-202	Clinical S CON
Q4W	every 4 weeks
SAE	serious adverse event
SAP	Statistical Analysis Plan
SD	stable disease
SNPs	single nucleotide polymorphisms
SUSAR	suspected unexpected serious adverse reaction
TCR	T-cell receptor
TEAE	treatment-emergent adverse event
Th1	T-helper type 1
TMB	tumor mutational burden
TSH	thyroid-stimulating hormone
ULN	upper limit of normal
WBC	white blood cells
WOCBP	women of childbearing potential

## **Appendix 7 Single Arm UV1 Cohort**

#### **Background and Rationale**

Patients participating in the Extended Exploratory cohort of the study (Appendix 2) provide biological sample material including PBMCs and tumor tissue to answer the exploratory objectives of the INITIUM study. The material is used to test for immune response in blood and to characterize changes in the tumor and the tumor microenvironment. The PBMCs and tumor tissue from patients in the experimental arm of the extended exploratory cohort is needed for these analyses, as this material is used to identify changes in the tumor environment that are unique for the vaccine responders.

As an immunological response to the vaccine is not expected in all patients in the experimental arm of the extended exploratory cohort, and as all patients in this arm will not be able to provide a complete set of biological sample material, 20 additional patients will be enrolled in a single arm UV1 cohort and provide additional biological material to support the extended exploratory cohort. This will be done to secure that sufficient material is available to identify anti-tumor activity unique for the vaccine responders and thereby to strengthen the support from the mechanistical data to the clinical outcome data derived from all patients in the study.

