UV1/h1ER1- MM-103/ US	Phase I open-label, multicenter study of UV1 and pembrolizumab 2-year follow-up	Unresectable or metastatic melanoma	30/	Dose: UV1 300 μg, sargramostim 37.5/75 μg (intradermal injection) Pembrolizumab according to label Week 1: Three UV1 vaccinations (D1, 3, 5) Weeks 2, 5, 8, 11, 14: One UV1 vaccination and pembrolizumab After Week 14: Pembrolizumab continued according to label

a) Enrollment and UV1 treatment is completed and patients are in follow-up

b) In the clinical study report, the first week of UV1 vaccination is referred to as "introduction week" and the week of first ipilimumab administration is "Week 1"

As of November 2019, 72 patients have received UV1 vaccinations in the context of clinical trials, and of these 68 patients have completed the UV1 vaccination therapy. The completed studies have shown that UV1 is generally safe and well tolerated. Common adverse events (AEs) related to UV1 include pruritus, erythema, fatigue, diarrhoea, pain, and rash. Serious AEs were reported in 18% of the patients, and related SAEs in 10%. A few patients (7%) have reported serious allergic reactions to the UV1 vaccination. Four prostate cancer patients and 1 patient with metastatic malignant melanoma experienced serious allergic reactions occurring within 3 to 30 minutes after injection of 9 or more doses of UV1 and sargramostim. All events resolved without sequelae.

Across the three Phase I/IIa studies conducted with UV1 vaccination, vaccine-specific T cells were induced in 78% (range 67% to 91%) of the patients. This supports the universal utility of the vaccine across different individuals and cancer types, and thus pre-screening of patients for human leukocyte antigen-type or other biomarkers before treatment with UV1 is not needed.

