In the study investigating the use of the UV1 vaccine in combination with ipilimumab in metastatic malignant melanoma patients, UV1-specific immune responses were induced in 91% of the patients. The vaccine-specific T cells appeared more frequently and rapidly in this study than in the studies investigating patients with prostate cancer and late-stage NSCLC, suggesting a synergistic effect of blocking of CTLA-4 and vaccination with UV1. Nine patients were evaluable for tumor response according to RECIST 1.1. Of these, 3 patients obtained a partial response (PR) as best overall response, 3 achieved stable disease (SD), and 3 experienced progressive disease (PD). The median PFS was 6.5 months and the 3-year survival rate was 67% (8/12).

The ongoing study combining UV1 and pembrolizumab in treatment of melanoma (UV1/hTERT-MM-103) has currently enrolled and treated 30 patients who are now in follow-up. Serious AEs and AEs of special interest (AESIs) are reported expedited to the sponsor and are the basis for the continuous safety assessment in this study. The collection of non-serious adverse is ongoing and will be reported when the study is completed, and all data have been finally verified. A thorough assessment of the safety profile of UV1 vaccination used in combination with pembrolizumab will include an evaluation of possible increase in frequency and severity of adverse reactions to pembrolizumab, the proportion of patients who have to terminate pembrolizumab treatment due to adverse reactions, and if the combination treatment enhances the UV1 related side effects.

Up to the date of this protocol, the safety information available from study UV1/hTERT-MM-103 include nine serious adverse events (SAEs) for 7 patients (23.3%) in the study, the majority of which were considered unrelated to study treatment. One SAE of grade 3 arthritis was assessed as possibly related to administration of UV1 vaccine and pembrolizumab, but the patient continued with treatment after resolution of the SAE. No AESIs (anaphylactic reaction, anaphylactic shock or hypersensitivity) have been reported among the patients. The number of UV1 vaccinations in this study is reduced to 8 compared to 12 to 18 in the completed Phase I studies as a measure to reduce the risk for serious allergic reactions following UV1 vaccination treatment.

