# 2.6 Rationale for Dose and Administration Regimen

Three Phase I/II studies investigating the use of UV1 vaccinations have been completed (n=52). One study in NSCLC and one study in prostate cancer were dose-finding studies comparing the safety of 100, 300, and 700  $\mu$ g UV1 using 75  $\mu$ g sargramostim per vaccination for up to 18 vaccinations. No dose-limiting toxicities were observed in doses up to 700  $\mu$ g. Signals of efficacy have been observed in all 3 studies in the form of vaccine-specific immune responses and PFS and OS which compares favorably to historical controls.

Across the 3 completed Phase I/II studies with UV1 vaccination, 78% (40/51) of the patients with samples available for analysis had detectable vaccine-specific immune response. A higher proportion of patients with vaccine-specific immune response was seen in the group of patients receiving the 300  $\mu$ g UV1 dose; 88% compared to 69% and 71% in the 100 and 700  $\mu$ g groups, respectively. In the study where 300  $\mu$ g UV1 was used in combination with ipilimumab in patients with melanoma, 91% of the patients showed an immune response to UV1.

No clear dose relationship was observed in the proportion of patients experiencing AEs, although a tendency towards a lower frequency of related AEs, injection site events, and Grade 3 events was observed in the 300- $\mu$ g dose group. Across the 3 studies, a total of 17 SAEs were reported, and 9 patients (17%) had related SAEs. Three patients had events that were related to ipilimumab, and 6 patients (12%) experienced 6 SAEs that were related to UV1 vaccination. Of these, 5 events in 5 patients (10%) were serious allergic reactions: anaphylactic reaction, anaphylactic shock, and hypersensitivity. Three events of serious allergic reactions occurred in the 700  $\mu$ g UV1 dose group, 2 in the 300  $\mu$ g UV1 dose group, and none in the 100  $\mu$ g UV1 dose group.

Taken together, the data on efficacy in terms of vaccine-specific immune response and safety related to dose of UV1 from the completed Phase I/II studies with UV1 support the use of the 300 µg UV1 dose for further clinical development of UV1.

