From signing of the Informed Consent Form (ICF) until the first dose of induction therapy, only AEs/SAEs caused by study-specific procedures should be reported. Non-serious AEs should be reported from the first dose of induction therapy until 30 days after the last dose of induction therapy, or until new anticancer treatment is initiated (whichever comes first). All SAEs should be reported from the first dose of induction therapy until 70 PFS events are reached, until 18 months post last patient randomized or until new anticancer treatment is initiated (whichever comes first). Adverse events and SAEs that are ongoing beyond the required reporting timelines shall be followed up locally per institutional practice until resolution or stabilization or the patient is lost to follow up.

During the study, an Independent Data Monitoring Committee (IDMC) will monitor safety information to ensure patient safety (refer Section 8.2.1).

Patients at selected sites will have the option to be included in the Extended Exploratory Cohort of the study (Appendix 2) provided that the cohort is still open for inclusion. This cohort of approximately 40 patients, randomized in a 1:1 ratio to either of the 2 treatment arms, will have additional sampling of blood, tissue, and feces for exploratory purposes (see Table 9 and Table 10). The biologic sampling will be in addition to blood samples planned for all patients in the study. Fecal samples will be collected in the Screening period while tumor biopsies (snap-frozen tissue and formalin fixated paraffin embedded tissue) will be harvested in the Screening period and at the safety follow-up visit. In the experimental arm, delayed-type hypersensitivity (DTH) response will be assessed at 5 timepoints during the study. A biobank will be established for current and future analysis of the samples collected.

In addition to the 2-armed part of the study, 20 patients will be enrolled in a single arm UV1 cohort for collection of additional biological material to support the Extended Exploratory Cohort of the study. The single arm UV1 cohort is intended for exploratory purposes only (Appendix 7 Single Arm UV1 Cohort).

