## 9.4.4 Exploratory Analyses

Biomarkers and parameters for immunological mode of action (eg, T-cell response) will be summarized per timepoint with descriptive statistics. The potential relationship between exploratory biomarkers and treatment response/immune response will be summarized using cross-tabulation (biomarker measured as present Yes/No) and level of biomarker (mean, standard deviation, median, minimum, and maximum) for each response group (biomarkers measured on continuous scales).

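### Immune response enters the biomarker analysis only as a group label; adding its measured size would recover precision that a responder/non-responder split gives away

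*Combined protocol and SAP*

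**What the plan says.** - **Purpose of the added patients.** Appendix 7 (Background and Rationale) says of the experimental-arm samples that "this material is used to identify changes in the tumor environment that are unique for the vaccine responders". Because not everyone will respond to the vaccine and not everyone will give a full set of samples, "20 additional patients will be enrolled in a single arm UV1 cohort".
- **Planned analysis.** Section 9.4.4 states: "The potential relationship between exploratory biomarkers and treatment response/immune response will be summarized using cross-tabulation (biomarker measured as present Yes/No"). For biomarkers on a continuous scale, the same sentence gives mean, standard deviation, median, minimum and maximum per response group. The Yes/No describes the biomarker. Immune response enters as the grouping.
- **Cohort size.** Section 4.1 describes the Extended Exploratory Cohort: "This cohort of approximately 40 patients, randomized in a 1:1 ratio to either of the 2 treatment arms". About 20 of its patients therefore receive UV1.
- **Earlier response rates.** Section 2.4 reports that vaccine-specific T cells "were induced in 78% (range 67% to 91%) of the patients". Section 2.6 gives the pooled figure as "78% (40/51) of the patients with samples available for analysis had detectable vaccine-specific immune response", and by dose, with the 300 µg group first, "88% compared to 69% and 71% in the 100 and 700" µg groups. For UV1 with ipilimumab in melanoma, Section 2.4 says "UV1-specific immune responses were induced in 91% of the patients".
- **Related plans.** The Appendix 2 endpoints include correlations of blood immune response, delayed-type hypersensitivity (DTH) and T-cell receptor change with clinical response. None relates immune response to change in the tumor.

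The documents state no expected response rate for this trial, no cut-off for a vaccine responder in blood, no planned number of non-responders and no precision target.

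**The concern.** Among vaccinated patients, saying that a tumor change belongs to vaccine responders takes a contrast with vaccinated patients who did not respond. Past rates make those patients the scarce group, and 20 further UV1 patients add few of them. A two-group summary also treats a weak and a strong responder alike, although most of the variation in response lies among responders. The likely result is an imprecise picture of whether stronger vaccine responses go with more change in the tumor. Patients give repeat biopsies and about 326 mL of extra blood for this work, and Appendix 7 wants the mechanistic data to support the clinical outcome data.

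**Working it through.** **Inputs.** UV1-treated patients: about 40/2 = 20 (Section 4.1) plus 20 (Appendix 7) = about 40. Response rate p: 67% (lowest study), 78% (pooled), 88% (300 µg group), 91% (with ipilimumab), from Sections 2.4 and 2.6.

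**The plan's own figure.** 40/51 = 78.4%, which reproduces the stated 78%. The plan gives no size calculation for the added cohort.

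**Step 1, non-responders.** 40 × (1 − p).

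**Step 2, information kept by a split.** If a normal response measure, linearly related to the biomarker, is cut so that a share p are responders, the share kept is φ(z_p)² / [p(1 − p)]. For p = 0.88: 0.200² / (0.88 × 0.12) = 0.040/0.1056 = 0.379.

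**Step 3, imbalance alone.** Without assuming an underlying continuous scale, efficiency against a 20:20 split is 4p(1 − p).

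| p | Non-responders of 40 | Kept by split | 40 are worth | Patients lost | Lost through imbalance alone |
|---|---|---|---|---|---|
| 67% | 13.2 | 59% | 23.7 | 16.3 | 4.6 |
| 78% | 8.8 | 51% | 20.4 | 19.6 | 12.5 |
| 88% | 4.8 | 38% | 15.2 | 24.8 | 23.1 |
| 91% | 3.6 | 32% | 12.9 | 27.1 | 26.9 |

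The loss in step 2 equals the 20 added patients at p = 79%; the loss in step 3 does so at p = 85%.

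**Step 4, sample loss.** Appendix 7 expects incomplete sample sets but gives no rate. If 60% to 80% are complete (assumption), non-responders range from 40 × 0.6 × 0.09 = 2.2 to 40 × 0.8 × 0.33 = 10.6.

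**Step 5, simulation as a yardstick.** No test is planned; power here only translates the information loss. With an assumed correlation of 0.45 and two-sided 5% (40,000 runs):

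- continuous response, 20 patients: 53%;
- continuous response, 40 patients: 85%;
- split response, 40 patients: 61%, 54%, 40% and 35% at p = 67%, 78%, 88% and 91%.

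**Step 6, assay floor.** Earlier responses are described as detectable or not, so non-responders may share one floor value. With all of them tied at the floor and an assumed correlation of 0.5 (4,000 runs), Spearman power with 40 patients is 86% to 88% over the four rates. The split (Mann-Whitney) gives 69%, 59%, 46% and 38%. Most of the gain comes from grading the responders.

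**The case against.** **Controls are available.** Appendix 2 frames the tumor infiltrate, mutational burden and T-cell receptor objectives against nivolumab plus ipilimumab, and Table 10 gives about 20 control patients the same paired biopsies and mononuclear-cell samples. A change seen in 0 of 4, 9 or 13 non-responders is compatible with a true rate up to 60%, 34% or 25% (1 − 0.025^(1/n)). Pooled with 20 controls, 0 of 24 or 0 of 33 brings that to 14% or 11%. This stands for vaccine specificity. It does not separate responders from non-responders among the vaccinated, since controls were never given the vaccine.

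**Correlations are already planned.** In part they are, but with clinical response, not with tumor change.

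**It is exploratory and descriptive.** That stands and limits the weight of the point. Section 9.4.1 also leaves detail to a separate SAP, which may already cover this.

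**The rates are historical.** That stands too. The 91% comes from a 12-patient study; if it is 10 of 11 (assumption), the exact 95% interval is 59% to 99.8%.

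**Stronger readings that the documents do not support.**

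- A reader might infer that the split cancels the 20 added patients. At 67% the loss is about 16, below 20, and on imbalance alone the statement fails at 78% as well.
- A reader might infer that the added cohort cannot meet its purpose. Appendix 7 seeks more responder material, and 20 more UV1 patients roughly double it (from 20p to 40p). It names no comparator, and the controls are there.
- A reader might take the Yes/No in Section 9.4.4 as a cut of the immune response. It refers to the biomarker.

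**Conclusion.** The point holds as a cheap improvement to an exploratory analysis. At the earlier response rates, about 40 UV1-treated patients give about 4 to 13 non-responders before sample loss. Treating response as two groups costs the equivalent of about 16 to 27 of the 40 patients, and about 25 to 27 at the two rates closest to this trial.

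The patient equivalents rest on a roughly normal underlying response, a linear relation to the biomarker and past rates carrying over. Counting imbalance alone, the loss runs from about 5 to 27, so the conclusion is firm at 88% to 91% and modest at 67%. Primary and secondary endpoints are untouched.

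**What to change.** In Section 9.4.4 and Appendix 7, or in the SAP to which Section 9.4.1 refers:

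1. Add, as the main immune-response analysis within UV1-treated patients, the relation between the size of the vaccine response and the change in tumor infiltrate, tumor mutational burden and T-cell receptor repertoire. Report a Spearman correlation or regression slope with a 95% confidence interval.
2. Define the size of the response in advance: the quantitative T-cell read-out at one named visit, if the assay provides one, and the DTH reaction size that patients already record.
3. Keep the responder/non-responder table as description, with group sizes shown and the responder definition stated.
4. Keep the comparison with control-arm samples for the question of vaccine specificity.

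**Cost.** Wording and a little extra analysis; no new patients, visits or samples. Inclusion in the single-arm cohort was planned to end in H1 2023, before this protocol version (September 2023), so the analysis is the practical place to gain precision. The main dependency is a quantitative T-cell assay, which the sponsor should confirm. DTH size is patient-measured, and testing stops when induction is discontinued early, so it is a second measure and not a full substitute.
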